5.2 Exclusion Criteria

Subject will be excluded from participation in the study if any of the following apply:

For all subjects:

1. Subject has preexisting sensory or motor neuropathy grade ≥ 2 .
2. Subject has active central nervous system (CNS) metastases. Subjects with treated CNS metastases are permitted on study if all the following are true:
 - CNS metastases have been clinically stable for ≥ 6 weeks prior to screening
 - If requiring steroid treatment for CNS metastases, the subject is on a stable dose ≤ 20 mg/day of prednisone or equivalent for ≥ 2 weeks
 - Baseline imaging scans show no evidence of new or enlarged brain metastasis
 - Subject does not have leptomeningeal disease
3. Subject has ongoing clinically significant toxicity (grade 2 or higher with the exception of alopecia) associated with prior treatment (including systemic therapy, radiotherapy or surgery).
4. Subjects with ongoing \geq grade 3 immunotherapy-related hypothyroidism or panhypopituitarism are excluded. Subjects with ongoing immunotherapy-related colitis, uveitis, myocarditis or pneumonitis, or subjects with other immunotherapy-related AEs requiring high doses of steroids (> 20 mg/day of prednisone or equivalent), are excluded. Subject with \leq grade 2 immunotherapy-related hypothyroidism or panhypopituitarism may be enrolled when well-maintained/controlled on a stable dose of hormone replacement therapy (if indicated).
5. Subject has a history of uncontrolled diabetes mellitus within 3 months before the first dose of study treatment. Uncontrolled diabetes (within 3 months before first dose) is defined as hemoglobin A1c (HbA1c) $\geq 8\%$ or HbA1c between 7 and $< 8\%$ with associated diabetes symptoms (polyuria or polydipsia) that are not otherwise explained. The lowest HbA1c during the screening period will be used to determine eligibility.
6. Subject has prior treatment with enfortumab vedotin or other monomethyl auristatin E (MMAE) based antibody-drug conjugates (ADCs).
7. Subject has a second malignancy diagnosed within 3 years before first dose of study drug, or any evidence of residual disease from a previously diagnosed malignancy. Subjects with non-melanoma skin cancer, localized prostate cancer treated with curative intent with no evidence of progression, low-risk or very low-risk (per standard guidelines)

- localized prostate cancer under active surveillance/watchful waiting without intent to treat, or carcinoma in situ of any type (if complete resection was performed) are allowed.
8. Subject is currently receiving systemic antimicrobial treatment for viral, bacterial, or fungal infection at the time of first dose of study treatment. Routine antimicrobial prophylaxis is permitted.
 9. Subject has known active hepatitis B (e.g., hepatitis B surface antigen [HBsAg] reactive) or active hepatitis C (e.g., hepatitis C virus [HCV] RNA [qualitative] is detected).
 10. Subject has known history of human immunodeficiency virus (HIV) infection (HIV 1 or 2).
 11. Subject has documented history of a cerebral vascular event (stroke or transient ischemic attack), unstable angina, myocardial infarction or cardiac symptoms (including congestive heart failure) consistent with New York Heart Association Class III-IV within 6 months prior to the first dose of study drug.
 12. Subject has major surgery within 4 weeks prior to first dose of study drug.
 13. Subject had radiotherapy, chemotherapy, biologics, investigational agents, and/or antitumor treatment with immunotherapy that is not completed 2 weeks prior to first dose of study drug.
 14. Subject has known hypersensitivity to enfortumab vedotin or to any excipient contained in the drug formulation of enfortumab vedotin (including histidine, trehalose dihydrate and polysorbate 20) OR subject has known hypersensitivity to biopharmaceuticals produced in Chinese hamster ovary cells.
 15. Subject has known active keratitis or corneal ulcerations. Subject with superficial punctate keratitis is allowed if the disorder is being adequately treated in the opinion of the investigator.
 16. Subject has any condition, which, in the investigator's opinion, makes the subject unsuitable for study participation.

Cohort 9: 1L HNSCC

17. Had PD within 6 months of completion of curatively intended systemic treatment for locoregionally advanced HNSCC.
18. Has had an allogeneic tissue/solid organ transplant.
19. Has severe hypersensitivity (\geq grade 3) to pembrolizumab and/or any of its excipients.
20. Has a history of (non-infectious) pneumonitis / interstitial lung disease that required steroids or has current pneumonitis / interstitial lung disease.
21. Has a history of idiopathic pulmonary fibrosis, organizing pneumonia, drug-induced pneumonitis, idiopathic pneumonitis, or evidence of active pneumonitis on screening chest CT scan.

22. Has a life expectancy of less than 3 months and/or has rapidly progressing disease (e.g., tumor bleeding, uncontrolled tumor pain) in the opinion of the treating investigator.
23. Active autoimmune disease that has required systemic treatment in past 2 years (i.e. with use of disease modifying agents, corticosteroids or immunosuppressive drugs).
 - a. Replacement therapy (e.g., thyroxine, insulin, physiologic corticosteroid replacement therapy for adrenal or pituitary insufficiency) is not considered a form of systemic treatment and is allowed.
 - b. Brief (<7 days) use of systemic corticosteroids is allowed when use is considered standard of care.
 - c. Subjects with vitiligo, psoriasis, type 1 diabetes mellitus, hypothyroidism, or resolved childhood asthma/atopy will not be excluded.
 - d. Subjects requiring intermittent use of bronchodilators, inhaled steroids, or local steroid injections will not be excluded.
 - e. Subjects with hypothyroidism that is stable with hormone replacement or Sjögren's syndrome will not be excluded.
24. Has an active infection requiring systemic therapy.
25. Has received prior therapy with an anti-PD-1 or anti-PD-L1 agent in the recurrent/metastatic setting. If anti-PD-1 or anti-PD-L1 agent was given as part of curative intent therapy, it must be at least 1 year since last dose.
26. Has received a live vaccine within 30 days of planned start of study therapy. Examples of live vaccines include, but are not limited to, the following: measles, mumps, rubella, varicella/zoster (chicken pox), yellow fever, rabies, Bacillus Calmette Guérin, and typhoid vaccine. Seasonal influenza vaccines for injection are generally killed virus vaccines and are allowed; however, intranasal influenza vaccines (e.g., FluMist®) are live attenuated vaccines and are not allowed.
27. Subject has active tuberculosis

5.3 Restrictions During the Study

Not applicable.

5.4 Screen Failures

A screen failure is defined as a subject who signed the ICF but did not meet one or more criteria required for participation in the study and was not enrolled.

For screen failures, the demographic data, date of signing the ICF, inclusion and exclusion criteria, AEs up to the time of screen failure and reason for screen failure will be collected in the electronic case report form (eCRF).

5.4.1 Rescreening

Results of screening assessments that do not meet the parameters required by eligibility criteria (e.g., clinical laboratory tests, vital signs, physical examination, ECG, etc.) may be repeated within the 28-day screening period without the need to register the subject as a

screen failure. If more than 28 days elapses from the date of signing the ICF, the subject must be documented as a screen failure. In order to re-screen, a new ICF must be signed and the subject entered into screening with a new subject identification number. Rescreening is only allowed once for an individual subject.

6 INVESTIGATIONAL PRODUCT(S)

6.1 Investigational Product(s) Administered

6.1.1 Enfortumab Vedotin

The investigational product, enfortumab vedotin (ASG-22CE), is a sterile, preservative-free, white to off-white lyophilized powder to be reconstituted for intravenous administration. The investigational product is supplied by Astellas in single-use glass vials containing 30 mg and/or 20 mg enfortumab vedotin in each vial. The investigational product should be stored at 2°C to 8°C.

Refer to the pharmacy manual, product label and package insert for detailed information regarding preparation, handling and storage of the enfortumab vedotin.

6.1.1.1 Dosing and Administration of Enfortumab Vedotin

Enfortumab vedotin at a dose of 1.25 mg/kg will be administered as an intravenous infusion over approximately 30 minutes on days 1, 8, and 15 of every 28-day cycle (days 1 and 8 of every 21-day cycle for cohort 9). In the absence of IRRs, the infusion rate for all subjects should be calculated in order to achieve an approximate 30-minute infusion period.

Enfortumab vedotin must not be administered as an intravenous push or bolus. Enfortumab vedotin should not be mixed with other medications. At least 7 days must elapse between doses of enfortumab vedotin.

Subject weight must be measured during all relevant assessment time points as described in the Schedules of Assessments [Table 1] and [Table 2]. Weight-based dosing is calculated using the subject's actual body weight on day 1 of each cycle. **An exception to weight-based dosing is made for subjects weighing greater than 100 kg; doses will be based on 100 kg for these individuals. The maximum dose permitted on this study is 125 mg.**

Subjects should be observed during enfortumab vedotin administration and for at least 60 minutes following the infusion for the first 3 cycles. All supportive measures consistent with optimal subject care should be given throughout the study according to institutional standards.

The injection site should be monitored closely for redness, swelling, pain, and infection during and at any time after administration. Subjects should be advised to report redness or discomfort promptly at the time of administration or after infusion. Events of extravasation should be managed per institutional guidelines and precautions should be taken to prevent extravasation per institutional standards.

6.1.2 Pembrolizumab (Cohort 9 Only)

Pembrolizumab injection is a sterile, preservative-free, clear to slightly opalescent, colorless to slightly yellow solution that requires dilution for IV infusion. Each vial contains 100 mg of pembrolizumab in 4 mL of solution. Each 1 mL of solution contains 25 mg of pembrolizumab and is formulated in L-histidine (1.55 mg), polysorbate 80 (0.2 mg), sucrose (70 mg), and Water for Injection, United States Pharmacopeia (USP). Pembrolizumab will be administered as a dose of 200 mg using a 30-minute intravenous infusion on day 1 of each 3-week cycle, approximately 30 minutes after completion of the enfortumab vedotin administration. Sites should make every effort to target infusion timing to be as close to 30 minutes as possible. However, given the variability of infusion pumps from site to site, a window between -5 minutes and +10 minutes is permitted (i.e., infusion time is 30 minutes (-5 min/+ 10 min)).

Pembrolizumab may be administered for a maximum of 35 cycles.

The pharmacy manual contains specific instructions for the preparation of the pembrolizumab infusion and administration of infusion solution.

6.2 Preparation/Handling/Storage/Accountability

6.2.1 Packaging and Labeling

Investigational products (enfortumab vedotin [ASG-22CE] and pembrolizumab) used in this study will be prepared, packaged and labeled under the responsibility of qualified personnel at APGD-Astellas US Technologies (AUST) or sponsor's designee in accordance with APGD-AUST or sponsor's designee standard operating procedures (SOPs), Good Manufacturing Practice (GMP) guidelines, International Council for Harmonisation of Technical Requirements for Pharmaceuticals for Human Use (ICH) Good Clinical Practice (GCP) guidelines and applicable local laws/regulations.

Each carton and vial will bear a label conforming to regulatory guidelines, GMP and local laws and regulations that identifies the contents as investigational drug.

Refer to the pharmacy manual for detailed information regarding packaging and labeling of the investigational products.

6.2.2 Handling, Storage and Accountability

1. The investigator or designee must confirm appropriate temperature conditions have been maintained during transit for all investigational products received and any discrepancies are reported and resolved before use of investigational products.
2. Only subjects enrolled in the study may receive investigational products and only authorized study site personnel may supply or administer investigational products. Only investigational products with appropriate expiry/retest dating may be dispensed.
3. All investigational products must be stored in a secure, environmentally controlled and monitored (manual or automated) area in accordance with the labeled storage conditions and access must be limited to the investigator and authorized study site personnel.

4. The investigator, institution or the head of the medical institution (where applicable) is responsible for accountability, reconciliation and record maintenance (i.e., receipt, reconciliation and final disposition records).
5. Further guidance and instruction on final disposition of used and unused investigational product is provided in the pharmacy manual.

Refer to the pharmacy manual for detailed information regarding handling, storage and accountability of the investigational products.

6.3 Randomization and Blinding

This is an open-label study. Subject enrollment and dispensation of investigational product will be performed via the interactive response technology (IRT) system. Prior to initiation of study treatment, study site personnel will obtain the subject number and medication assignment from the IRT system. Specific IRT procedures will be described in the respective study manual.

6.4 Investigational Product Compliance

The dose and schedule of enfortumab vedotin and pembrolizumab administered to each subject will be recorded on the eCRF for each dose. Reasons for dose delay, reduction or omission will be documented. Dosing noncompliance for enfortumab vedotin of less than or greater than 10% from each intended dose will be considered a major protocol deviation. Dosing noncompliance for pembrolizumab of 1000 mg or greater will be considered a major protocol deviation.

6.5 Previous and Concomitant Treatment (Medication and Nonmedication Therapy)

If the investigator determines that any of the following medications are necessary to provide adequate medical support to the subject, the subject must be withdrawn from further administration of the study treatment:

- Other investigational drugs
- Chemotherapy or other medications intended for antitumor activity. This does not apply to subjects on endocrine therapy, or to subjects on agents intended for the treatment of bone metastasis where subjects should be on a stable dose of bone targeting agents for at least 2 weeks prior to study entry (e.g., bisphosphonates, or receptor activator of nuclear factor kappa-B [RANK] ligand inhibitors).
- Radiation therapy except palliative radiation for nontarget lesions that is approved by the sponsor. Note: Radiation therapy to a preexisting symptomatic solitary lesion or to the bone may be considered on an exceptional case-by-case basis after consultation with the sponsor. The radiated lesion must be a nontarget lesion per RECIST Version 1.1 and the subject must have clear measurable disease outside the radiated field. Enfortumab vedotin may not be given concurrently with radiation therapy.
- Subjects who are receiving strong cytochrome P450 (CYP)3A4 inhibitors concomitantly with enfortumab vedotin should be closely monitored for adverse reactions.

- For cohort 9: Live or attenuated vaccines within 30 days prior to the first dose of study treatment and while participating in the study.
- For cohort 9: Systemic glucocorticoids except when used for the following purposes:
 - To modulate symptoms of an AE that is suspected to have an immunologic etiology
 - For the prevention of emesis
 - To premedicate for IV contrast allergies
 - To treat COPD exacerbations (only short-term oral or IV use in doses > 10 mg/day prednisone equivalent)
 - For chronic systemic replacement not to exceed 10 mg/day prednisone equivalent
 - For topical use or ocular use
 - Intraarticular joint use
 - For inhalation in the management of asthma or chronic obstructive pulmonary disease.

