 - For inhalation in the management of asthma or chronic obstructive pulmonary disease.

Duration of Treatment:

Subjects will be allowed to receive enfortumab vedotin (and pembrolizumab for cohort 9) until treatment discontinuation criteria are met.

Statistical Methods:

Sample Size Justification:

The planned sample size for cohorts 1 to 8 is 40 subjects in each cohort. Assuming the ORR of current standard of care (reference ORR for the 7 tumor types chosen for the study) ranges from 10% to 20%, and at least a 10% absolute increase in ORR is considered clinical meaningful improvement, the sample size of 40 subjects allows to have 80% confidence interval of ORR for the study drug to exclude the reference ORR.

The planned sample size for cohort 9 is 40 subjects. Assuming the reference ORR for cohort 9 is 20%, and at least a 25% absolute increase in ORR is considered clinical meaningful improvement for combination therapy, the sample size of 40 subjects allows a 92% power to detect a statistically significant difference at type 1 error rate of 1-sided 0.025.

Efficacy:

Confirmed ORR (CR+PR) and DCR (CR+PR+SD) as per RECIST Version 1.1 will be calculated and the corresponding 95% confidence intervals will be constructed based on Clopper-Pearson method for each tumor type. For cohort 9, analyses will also be calculated based on iRECIST. Other efficacy endpoints, including DOR, PFS and OS will be summarized using Kaplan-Meier method. Efficacy analysis will include all subjects who were treated and with evaluable tumor response data upon analysis cutoff date.

Safety:

The Safety Analysis Set (SAF) will be used for the safety analysis. All subjects who are enrolled and received study drug will be included in the SAF. The frequency of AEs and the serious AEs will be summarized by MedDRA system organ class (SOC) and preferred term. In addition, summary statistics will be provided for the following safety parameters:

- Laboratory values
- Vital sign measurements
- ECOG performance status

Pharmacokinetics:

Descriptive statistics (e.g., number, mean, standard deviation, minimum, median, maximum, coefficient of variation and geometric mean) will be provided for serum or plasma concentrations of enfortumab vedotin and MMAE. Additional model-based analyses and exposure response may be performed and reported separately.

Pharmacodynamics | Immunogenicity:

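### In cohort 9, exclusion 2 admits subjects on a stable steroid dose for treated CNS metastases, but Section 6.5 ends study treatment if that steroid is still needed once dosing starts

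*Protocol*

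**What the plan says.** Protocol Section 5.2 places exclusion 2 in the block that applies to all subjects, so it governs cohort 9 too. Active CNS metastases exclude a subject, but "Subjects with treated CNS metastases are permitted on study if all the following are true". One of those conditions deals with steroids: "If requiring steroid treatment for CNS metastases, the subject is on a stable dose", capped at 20 mg/day prednisone equivalent and held for at least 2 weeks. The CNS disease must also have been clinically stable for at least 6 weeks before screening.

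Protocol Section 6.5 lists treatments which, if the investigator judges them necessary, mean that "the subject must be withdrawn from further administration of the study treatment". One entry reads "For cohort 9: Systemic glucocorticoids except when used for the following purposes". Eight purposes follow. They include "For chronic systemic replacement not to exceed 10 mg/day prednisone equivalent" and end with "For inhalation in the management of asthma or chronic obstructive pulmonary disease". Synopsis 1.1 carries the same entry and the same eight purposes.

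**The concern.** Both rules are current text and both apply to the same cohort 9 subject, one at entry and the other during treatment. The first accepts a subject because a steroid dose for CNS disease is stable. The second has no place for that steroid and makes its continued need a reason to stop study treatment. A site that follows both could dose an eligible subject and then have to stop, or keep treating and record a major deviation. Two sites could handle the same patient differently without either misreading the protocol.

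**Working it through.** The plan states no figure on this point, so the check compares the texts and counts the listed items.

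**1. Does any cohort 9 criterion narrow exclusion 2?**
- Inclusions 47 to 53 do not mention steroids.
- The cohort 9 exclusions run from 17 to 27, which is 27 − 17 + 1 = 11 criteria. Two mention steroids.
- Exclusion 20 concerns lung disease: "Has a history of (non-infectious) pneumonitis / interstitial lung disease that required steroids".
- Exclusion 23 concerns autoimmune disease. Its sub-item b says that brief (under 7 days) "use of systemic corticosteroids is allowed when use is considered standard of care". That qualifies the autoimmune exclusion and does not describe a dose held stable for 2 weeks or more.
- So 0 of 11 limit steroids given for CNS metastases. Among the criteria for all subjects, exclusion 4 also sets a steroid limit, but only for immunotherapy-related events.

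**2. Does any exception in 6.5 cover the use?**
- Systemic use (5): symptoms of a suspected immune-related AE; prevention of emesis; premedication for contrast allergy; short-term treatment of COPD exacerbation; chronic replacement up to 10 mg/day.
- Local or inhaled use (3): topical or ocular; intraarticular; inhaled for asthma or COPD.
- Total 5 + 3 = 8. Number covering treatment of CNS metastases: 0.

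**3. Could the nearest exception be stretched?** Replacement therapy is a different purpose from treating CNS metastases. Even if that exception were read as any chronic dose up to 10 mg/day, exclusion 2 admits doses up to 20 mg/day. The range above 10 and up to 20 mg/day would remain uncovered.

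**4. When does the conflict arise?** Section 6.5 acts only when the investigator determines that the drug is necessary, and it stops further dosing. Exclusion 2 describes status at entry and does not say that the steroid continues. A subject who has tapered off by cycle 1 day 1 meets both rules. The conflict is confined to subjects whose need continues once dosing starts.

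**5. What follows for such a subject?** Either study treatment stops, or it continues with a PD4 major deviation, the category in Section 10.3 for prohibited concomitant treatment. Section 10.3 also rules out protocol waivers, so no prior approval can reconcile the two rules.

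**6. Does this reach the analysis?** Under Section 7.1.1, cohort 9 subjects who stop treatment for reasons other than progression continue to be scanned. The FAS and RES definitions (Sections 9.2.1 and 9.2.2) contain no condition on protocol deviations, so the subject stays in both sets if otherwise qualified.

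**The case against.** The best defence is that the two rules can be read together. Exclusion 2 is a general entry rule; the cohort 9 entry in 6.5 is later in effect, more specific and stricter. A careful site would see that the subject will need a prohibited steroid and would not enrol. Exclusion 16, which turns on the investigator's opinion of suitability, gives it the means. This stands in part: immediate withdrawal is one possible path, not the necessary one. But exclusion 16 is discretionary. It permits the right outcome without requiring it and leaves room for sites to differ.

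A second defence is that the list in 6.5 is loosely drafted. Under the same withdrawal sentence it includes strong CYP3A4 inhibitors, for which it asks only for close monitoring, and the discontinuation reasons in Section 8.1 do not name steroids. Not every entry can be a literal withdrawal trigger. The glucocorticoid entry, however, fits the opening sentence, and its exceptions have little purpose unless other uses are barred.

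A third is that 6.5 is aimed only at drugs started on study. The same list makes room for treatment already under way at entry, such as bone-targeting agents on a stable dose. Where a baseline drug was meant to continue, the list says so, and it does not say so here.

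Stronger readings are tempting but unsupported. A reader might infer that every cohort 9 subject who enters on a steroid for CNS metastases must be withdrawn; step 4 shows that this needs a continuing need. A reader might take the repeat brain scans in Section 7.1.1 as proof that the case was foreseen; that text contemplates brain metastases in cohort 9 and says nothing about steroids. The bar on waivers in Section 5 concerns eligibility criteria, which this subject meets, so only Section 10.3 is relevant.

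**Conclusion.** The inconsistency is real and minor. For a cohort 9 subject with treated CNS metastases whose steroid is still necessary after dosing starts, Section 5.2 allows entry and Section 6.5 requires withdrawal from study treatment. No other cohort 9 criterion settles the matter.

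Its size cannot be computed. SAP Section 6.2.3 lists brain metastases among the baseline disease history, but neither document gives a count, or a count of those on steroids. The number is probably very small; that is a judgement, not a figure from the documents. A reader might infer harm to the primary endpoint or the decision rule. The documents do not show it: scans continue after such a withdrawal, membership of the FAS and RES does not depend on deviations, and no effect on power or the BOP2 boundaries is claimed. What is at stake is how an individual subject is treated, and whether sites handle and report the same case alike.

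The conclusion assumes that the eight purposes in 6.5 are a closed list, as their wording indicates.

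**What to change.** Make the sections agree. The preferred change is a cohort 9 limit in exclusion 2, so that subjects who need ongoing systemic steroids for CNS metastases outside the 6.5 exceptions are screened out before dosing. This matches the stricter cohort 9 rule already in 6.5. It costs one line and slightly narrower eligibility.

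If the sponsor wants to allow this use with pembrolizumab, leave exclusion 2 as it is. Instead add the stable dose for treated CNS metastases, with its 20 mg/day cap, to the cohort 9 exceptions in both 6.5 and synopsis 1.1. That costs one line in each place. The clinical choice between the two is the sponsor's. Neither needs new procedures or data.
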